8.2.5.1.2. Secondary Efficacy Endpoints

Additionally, symptom improvement will be evaluated by assessing changes in the secondary outcome measures: C-SSRS, Concise Health Risk Tracking –Clinician, -Self-Rated (CHRT-C and –SR), and BISS. These measures will be assessed at the times specified on the Schedule of Study Activities, Table 3.

The C-SSRS (and the retrospective Columbia-Classification Algorithm of Suicide Assessment (C-CASA component), Suicide Ideation and Behavior Questionnaire (SIBQ), BPRS, CHRT-C and –SR, will be evaluated within and between study treatment groups. Mean changes from baseline for the differences from baseline and after randomization baseline will be evaluated using a paired t-test within each study group and an unpaired t-test for K/N vs. K/L and K/P.

8.2.5.1.3. Diagnostic Metric

The following diagnostic metric will be evaluated at baseline:

- MINI 7.0.2

8.2.5.1.4. Additional Endpoints

The following additional endpoints will be recorded and analyzed for both study stages:

- Study dose per treatment group
- All-cause discontinuation (and reason for discontinuation)
- Suicide rates
- Incidence of hospitalization and ER visits for disease-related outcomes
- Proportion of subjects who are treated with new SSRIs or have increased SSRI dosages
- Proportion of subjects who discontinue SSRIs or have reduced SSRI dosages.

8.2.5.2 Safety Endpoints

8.2.5.2.1. Overall Adverse Events

Separate safety analyses will be performed for the two stages for the Safety population. Safety endpoints will include adverse events (AE), vital signs, and relevant clinical chemistries and hematology parameters.

The principle of treatment emergence will be employed for the analysis of AE data. Treatment emergence is defined to be any event that occurred during the observation period and was not present at baseline, or one which represents an exacerbation of a condition present at baseline.

Events emerging during ketamine treatment will be counted during the randomized phase of the study if not resolved by the start of randomized treatment initiation. Unresolved AE outcomes at the end of randomized treatment will be followed for an additional seven days or until resolution, whichever occurs earlier.

Adverse events will be classified by MedDRA. For each study treatment, safety data will be collected and analyzed per stage or until treatment-emergent AEs are resolved. The type, incidence, timing (onset, duration), relationship, and severity of AEs will be reported for treatment-emergent and suspected adverse reactions. Reasons for withdrawal due to AEs will also be reported. Narratives will be written for every AE classified as serious or associated with death. Safety results will be displayed separately for each stage and combined.

Safety and tolerability will be assessed using two-sided Fisher Exact tests to compare K/N vs. K/L and K/P. Mean changes from baseline will be displayed for each serum chemistry and hematology parameter as well as the shift; unpaired t-tests will be used to compare K/N vs. K/L and K/P; in addition, paired t-tests will be performed for the changes from baseline for each study treatment group.

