13.7 Safety Endpoints

13.7.1 Overall Adverse Events

Separate safety analyses will be performed for the two stages for the Safety population. Safety endpoints will include adverse events (AE), vital signs (VS), and relevant clinical chemistries and hematology parameters.

The principle of treatment emergence will be employed for the analysis of AE data. Treatment emergence is defined to be any event that occurred during the observation period and was not present at baseline, or one which represents an exacerbation of a condition present at baseline.

Events emerging during Stage 1 will be counted during Stage 2 if not resolved by the start of randomized treatment initiation. Unresolved adverse event outcomes at the end of Stage 2 will be followed for an additional seven days or until resolution, whichever occurs earlier.

Adverse events will be classified by MedDRA. For each study treatment, safety data will be collected and analyzed per stage or until treatment-emergent adverse events are resolved. The type, incidence, timing (onset, duration), relationship, and severity of AEs will be reported for

treatment-emergent and SARs. Reasons for withdrawal due to AEs will also be reported. Narratives will be written for every AE classified as serious or associated with death. Safety results will be displayed separately for each stage and combined.

Safety and tolerability will be assessed using two-sided Fisher Exact tests to compare K/N vs. K/L and K/P. Mean changes from baseline will be displayed for each serum chemistry and hematology parameter as well as the shift; unpaired t-tests will be used to compare K/N vs. K/L and K/P; in addition, paired t-tests will be performed for the change from baseline for each study treatment group.

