13.10.3 Conventions

Means, mean changes, standard deviations, and ranges will be presented separately for Stage 1 and then for each Stage 2 treatment group over time. These endpoints will be evaluated within the three study treatment groups for the change from Stage 1 and Stage 2 baselines using a paired t-test and between study treatment groups using an unpaired t-test at each time; these p-values will be presented as descriptive statistics.

For continuous variables, the mean, standard deviation, minimum, median and maximum will be presented, together with the total number of observations and the number of missing and non-missing values. Unless otherwise specified minimum and maximum values will be reported to the same number of decimal places as the recorded measurements, mean and median are reported to one more decimal place and standard deviation one additional decimal place more than the mean.

For ordinal and categorical variables, absolute and relative frequencies will be reported. Relative frequencies will be based on all observations and reported as percentages to one decimal place. Unless otherwise specified percentages will be based on the number of subjects with data and will not be calculated for missing categories.

Adverse events, medical histories and concomitant medications will be reported on a subject and an event basis. The percentages will be calculated using the number of subjects in the population Analysis Set as the denominator.

All hypotheses will be tested at 5% (final analysis) level of significance using a two-sided test unless otherwise specified.

P-values will be rounded to four decimal places. If a p-value is less than 0.0001 it will be reported as “<0.0001.” If a p-value is greater than 0.9999 it will be reported as “>0.9999”.

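### Ketamine-stage adverse events still open at randomisation count as Stage 2 events without having worsened, which dilutes the adverse-event comparison of NRX-101 with its controls

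*Combined protocol and SAP*

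**What the plan says.** The carry-over rule appears twice. Section 8.2.5.2.1: "Events emerging during ketamine treatment will be counted during the randomized phase of the study if not resolved" by the time randomised treatment starts. Section 13.7.1: "Events emerging during Stage 1 will be counted during Stage 2 if not resolved by the start of randomized treatment initiation". Neither sentence makes worsening a condition.

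Just before the rule, both sections define a treatment-emergent event as "any event that occurred during the observation period and was not present at baseline, or one which represents an exacerbation of a condition" already there at baseline. They do not say which baseline applies to Stage 2 events. Other parts of the plan recognise two: section 13.10.3 evaluates endpoints "for the change from Stage 1 and Stage 2 baselines using a paired t-test", and section 13.10.8 does the same for vital signs and ECGs.

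The between-arm test is also given in 8.2.5.2.1: "Safety and tolerability will be assessed using two-sided Fisher Exact tests to compare K/N vs. K/L and K/P". Section 13.10.8 sets out the adverse-event analyses again, with a Fisher test of overall incidence and a Poisson model for surveillance findings, and does not limit either to events that start after the first randomised dose. Results are to be shown for each stage and for both together.

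**The concern.** A Stage 2 comparison should show what the randomised drugs do. An event that started after the ketamine infusion and is unchanged at the first capsule cannot have been caused by that capsule. Counting it adds the same expected background to all three arms and moves the contrast toward no difference. It also places a ketamine event in the tables under NRX-101, lurasidone or placebo.

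For a safety comparison this is the less cautious direction of error. The plan itself notes that only 21 subjects have taken d-cycloserine at the 1000 mg dose in formal psychiatric studies (8.2.5.2.3 and 16.2), so the Stage 2 adverse-event table will be an important source on the combination. The control arms have 31 subjects each, which leaves little power to spare.

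**Working it through.** The plan states no adverse-event rate, no carry-over share and no power for this comparison, so there is no figure of its own to reproduce beyond the arm sizes.

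**Inputs from the documents**
- Arm sizes (13.8.1): 124 randomised 2:1:1, that is 124 × 2/4 = 62 on K/N and 124/4 = 31 on each control. All are taken as dosed.
- Test: two-sided Fisher's exact (8.2.5.2.1, 13.7.1). Level: "All hypotheses will be tested at 5% (final analysis) level of significance using a two-sided test unless otherwise specified" (13.10.3).

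**Assumptions**
- p is the true incidence of events starting after the first randomised dose.
- c is the share of subjects with a ketamine event open at that dose. It is equal across arms in expectation because of randomisation, and independent of new events.

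**Formulas**
- Observed incidence = c + (1 − c)p.
- Observed risk difference = (1 − c) × true difference.
- The same amount c(1 − p) is added in each arm. It is larger where p is smaller, so the risk ratio moves toward 1.

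**Example, 40% vs 10%, c = 10%**
- K/N: 0.10 + 0.90 × 0.40 = 0.46.
- Control: 0.10 + 0.90 × 0.10 = 0.19.
- Difference 27 points instead of 30; ratio 0.46/0.19 = 2.42 instead of 4.00.

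**Exact Fisher power, 62 vs 31, by full enumeration**

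| True rates | c = 0 | 2% | 5% | 10% | 20% |
|---|---|---|---|---|---|
| 40% vs 10% | 88.2% | 84.6% | 79.4% | 71.8% | 59.1% |
| 30% vs 10% | 58.4% | 53.8% | 47.3% | 38.4% | 29.1% |
| 40% vs 20% | 45.1% | 42.8% | 40.0% | 36.2% | 29.8% |
| 50% vs 20% | 80.7% | 78.5% | 75.3% | 69.9% | 58.7% |

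The c = 0 column is what the test would have if only events starting or worsening after the first randomised dose were counted.

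**Type I error.** With a true rate of 30% in both arms, the rejection rate is 3.8% at c = 0, 4.1% at c = 10% and 4.6% at c = 20%. It stays below 5%: the rule dilutes and does not create false positives.

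**The case against.** Five points can be made for the plan.

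1. **The carry-over share may be small.** The CADSS and BPRS schedule in section 8.1.4 ends at 4 hours, release after the 4-hour measurements needs pre-treatment vital signs or clinical stability, and only 24-hour responders are randomised. This is suggestive, not decisive. At c = 2% the loss for 40% vs 10% is under 4 percentage points.

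2. **Arm size is the larger limit for moderate harms.** At 20% vs 10%, power is 17% without carry-over and 13% at c = 10%. This stands. A reader might infer that the rule hides harms the trial would otherwise detect. The documents do not support that, because they give neither the rates nor the share.

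3. **The model fits any-event incidence, or terms that ketamine also causes.** If incidence is compared by MedDRA term, a harm that ketamine does not share is not diluted. This stands.

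4. **The rule need not contradict the definition of treatment emergence.** A reader might infer a plain self-contradiction. It is one only if baseline means the Stage 2 baseline. If it means pre-ketamine status, the rule is coherent, and section 4.6 does describe the therapy as a sequence that starts with ketamine. The documents support an undefined baseline and no more. On either reading, though, the events enter the between-arm test.

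5. **The consequences are bounded.** Safety tests are outside the hierarchy in 13.9; onset, duration and relationship are reported; start and stop times are collected; a DSMB reviews safety every 4 months; and the laboratory, ECG and rating-scale comparisons do not use the rule. All true, but none of it takes the carried-over events out of the Fisher test.

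Equal inflation of the arms also holds only in expectation. With 62, 31 and 31 subjects, chance imbalance can go either way and adds noise.

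**Conclusion.** The concern holds as a dilution of the Stage 2 adverse-event comparison. The rule is in the current text in two sections, requires no worsening, and nothing in 13.10.8 or elsewhere removes the carried-over events from the test of K/N against K/L and K/P. The direction follows for any c above zero: in expectation, higher incidence in each arm, a risk difference multiplied by (1 − c), and a risk ratio nearer 1.

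The size is not known. At 40% vs 10% the loss runs from about 4 percentage points of power at c = 2% to 29 at c = 20%; every rate and share behind those figures is assumed. The supported statement is that the rule dilutes, and may mask, a difference in any-event incidence or in terms that ketamine also causes. The change is still worth making, because the comparison gains nothing from the carried-over events, which the Stage 1 and combined displays can show, and because the fix is cheap.

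**What to change.** Amend sections 8.2.5.2.1, 13.7.1 and 13.10.8 together:

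- Define the Stage 2 adverse-event baseline as the subject's status just before the first dose of randomised drug.
- Base the between-arm Stage 2 incidence tests on events with onset, or worsening in severity, after that dose.
- List Stage 1 events that are ongoing and unchanged at that point separately by arm, and keep them in the Stage 1 and combined displays.
- Count each event once in the combined display; the plan does not now say whether a carried-over event would appear twice.

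Start and stop dates and times are already collected (12.2), so onset can be placed before or after the first dose. The intensity item in 12.2 allows a maximum, a single value or changes, so confirm that the eCRF dates changes in intensity; the worsening criterion needs this. The cost is one extra listing and possibly one eCRF field, with no change to visits, procedures or sample size.

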8.2.5.2.2. Safety Measures

The Patient Rated Inventory of Side Effects (PRISE), CADSS, and Barnes Akathisia Scale (BARS) (including the global severity rating) will be evaluated within and between study treatment groups. Mean changes from baseline for the differences from baseline and after randomization baseline will be evaluated using a paired t-test within each study group and an unpaired t-test for K/N vs. K/L and K/P.

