not clinically significant and recorded on the eCRF. Abnormal and clinically significant lab values will be reported as AEs if they fulfill any of the SAE criteria or are the reason for discontinuation of treatment with the study drug. Abnormal lab values (clinically significant and clinically non-significant), will be reviewed monthly by the medical monitor for trends. Should any abnormal lab values exceed rates described in the IB, the FDA and SPONSOR will be notified within regulatory timelines. McNemar paired comparison tests will be performed within study treatment groups for the abnormal percents while two-sided Fisher Exact tests will be performed between treatment groups.

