13.10.8 Safety Endpoints

Separate safety analyses will be performed for Stage 1, Stage 2, and combined across stages.

Adverse events will be classified by MedDRA. For each study treatment, safety data will be collected and analyzed while on Stage 1 or Stage 2 treatment or until treatment-emergent adverse events are resolved. The type, incidence, timing (onset, duration), relationship, and severity of AEs will be reported for treatment-emergent and SAEs. Reasons for withdrawal due to AEs will also be reported. Narratives will be written for every AE classified as serious or associated with attempted suicide or death.

Planned surveillance findings according to the designated safety monitor will also be analyzed. Adverse event timing will be displayed graphically. Overall incidence will be compared using a two-sided Fisher Exact test. The cumulative number of such episodes will be evaluated using a Poisson regression model to compare study treatment groups controlling for C-SSRS 24 hours post infusion (1, 2), age (<25, 25-39, >40), and gender.

Vital signs and ECGs (means and mean changes from Stage 1 and Stage 2 baselines) will also be evaluated within treatment groups using paired t-tests and between study treatment groups using unpaired t-tests. Percents with abnormal vital signs, heart rate, QRS duration, PR interval, RR interval, QT, and QTcF will be reported. McNemar paired comparison tests will be performed within study treatment groups for the abnormal discordant percents while two-sided Fisher Exact tests will be performed to compare incidences between treatment groups.

Blood draws for chemistries and hematologies will be evaluated within and between study treatment groups. Abnormality rates will be presented relative to established site-specific normal ranges and whether or not the abnormality is clinically significant. McNemar paired comparison tests will be performed within study treatment groups for the abnormal percents while two-sided Fisher Exact tests will be performed to compare incidences between treatment groups.

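### Between-arm comparisons of continuous safety measures use unpaired t-tests with no baseline covariate; the tests are valid, but baseline adjustment would usually be more precise, and the laboratory Fisher tests should say that they count new abnormalities

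*Combined protocol and SAP*

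**What the plan says.** **Continuous measures.**
- Laboratory parameters (Section 8.2.5.2.1, repeated in 13.7.1): "Mean changes from baseline will be displayed for each serum chemistry and hematology parameter as well as the shift; unpaired t-tests will be used". The sentence goes on to name the contrasts: "unpaired t-tests will be used to compare K/N vs. K/L and K/P; in addition, paired t-tests will be performed for the changes from baseline".
- PRISE, CADSS and BARS (Section 8.2.5.2.2): mean changes are "evaluated using a paired t-test within each study group and an unpaired t-test for K/N vs. K/L and K/P". Section 13.7.2 is similar. Section 8.2.6.2 describes the PRISE t-tests without mentioning change.
- Vital signs and ECG intervals, including QTcF (Section 13.10.8): means and mean changes are "evaluated within treatment groups using paired t-tests and between study treatment groups using unpaired t-tests".

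**Abnormal values.** In Section 8.2.5.2.3, McNemar tests are run within arms on the percentages abnormal, and "two-sided Fisher Exact tests will be performed between treatment groups". Section 13.10.8 says that the Fisher tests compare incidences, and does not define that word. Abnormality is judged against site-specific normal ranges.

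**Where baseline is already used.** Change scores subtract it. Laboratory shifts are displayed. Adverse events are counted only if treatment-emergent. Paired tests are run within arms. The efficacy MMRM has the baseline of the analysed variable as a fixed effect (Sections 11, 13.10.4 and 13.10.6). The Poisson model for surveillance episodes adjusts for 24-hour C-SSRS, age and gender.

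**The concern.** A t-test on change fixes the slope of follow-up on baseline at 1. When the true slope is lower, part of any chance baseline difference between arms passes into the estimated treatment difference, and the interval is wider than it needs to be. The control arms are small (31 randomised and 28 evaluable in each, Section 13.8). The protocol also says that only 21 subjects have had DCS at 1000 mg in formal psychiatric studies, so precision on safety has value here. The sponsor already adjusts for baseline in the efficacy models, so leaving it out for safety is inconsistent.

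For abnormality rates, a subject who is already out of range at baseline and stays there adds an event that has nothing to do with treatment. Such subjects enter every arm at about the same rate and dilute a real difference. This can happen for laboratory values because the entry limits in Table 2 are looser than normal ranges. For example, ALT, GGT and alkaline phosphatase are exclusionary only above 3 times the upper limit, uric acid above 1.5 times and creatinine above 1.3 times. Exclusion 22 sets 2.5 times for liver tests, which is still above normal.

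**Working it through.** **Plan's nearest figure.** No SD, power or sample size is given for any safety comparison. The closest is Table 13 (secondary efficacy): two-group t-test, two-sided 0.05, 90% power, effect size 0.754. With the 56 and 28 evaluable subjects of Section 13.8.3:

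(1.960 + 1.282) × √(1/28 + 1/56) = 3.242 × 0.2315 = 0.750 (normal approximation); 0.759 with the noncentral t.

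The stated 0.754 is reproduced. It confirms the arm sizes behind the t-test but says nothing about safety variances.

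**Inputs not in the documents.** These are the correlation r between baseline and follow-up and the ratio k = follow-up SD / baseline SD. I assume r from 0.3 to 0.9, and k = 1 first.

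**Equal SDs (σ).** Per-subject variances:
- change score: 2σ²(1-r)
- ANCOVA: σ²(1-r²)
- ratio: (1+r)/2, so the reduction is (1-r)/2

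The detectable difference at 90% power with 56 vs 28, in follow-up SDs, is 0.750 × √(2(1-r)) for change and 0.750 × √(1-r²) for ANCOVA.

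| r | Variance reduction | Detectable, change | Detectable, ANCOVA |
|---|---|---|---|
| 0.3 | 35% | 0.89 | 0.72 |
| 0.5 | 25% | 0.75 | 0.65 |
| 0.7 | 15% | 0.58 | 0.54 |
| 0.8 | 10% | 0.47 | 0.45 |
| 0.9 | 5% | 0.34 | 0.33 |

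A simulation of 20,000 trials per r at 28 vs 56 gave reductions of 34%, 25%, 14%, 9% and 4%. Type I error was about 5% for both methods. The one degree of freedom costs about 1% of variance at N = 84.

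**Unequal SDs.** With baseline variance 1, the change score has variance 1 + k² - 2rk and ANCOVA has k²(1-r²). The difference is (1 - rk)², which is never negative and is zero when rk = 1.
- k = 1.25: reduction 22%, 11%, 2% and 0% at r = 0.3, 0.5, 0.7 and 0.8.
- k = 0.8: reduction 36% to 50% over r = 0.3 to 0.9.

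**Abnormality rates (illustration only; all rates assumed).** Take 62 vs 31 subjects, new abnormality in 25% vs 5% of those normal at baseline, and a fraction b abnormal at baseline who all stay abnormal. Counting everyone, the rates are b + (1-b) × 0.25 and b + (1-b) × 0.05. At b = 20% these are 40% and 24%. Exact two-sided Fisher power:

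| b | All subjects | Baseline-normal only |
|---|---|---|
| 0% | 67% | 67% |
| 2% | 62% | 65% |
| 5% | 54% | 63% |
| 10% | 44% | 59% |
| 20% | 29% | 55% |

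The direction is clear. The size depends entirely on b and on persistence.

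**Which baseline.** Section 8.2.1, Table 4 and Table 3 give pre-treatment chemistry and CBC at screening only. Section 8.2.5.2.3 adds Visit 1. Section 13.10.8 refers to Stage 1 and Stage 2 baselines. As Table 3 reads, BARS is rated at ketamine dosing and then not until Day 7. CADSS is rated only at dosing and 4 hours, so no Stage 2 comparison of it is possible with either method.

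**The case against.** The strongest reply is that nothing here is an error. Under randomisation a t-test on change is unbiased, regression to the mean acts equally on all arms in expectation, and the standard error already covers chance imbalance. That stands. The safety tests are also outside the testing hierarchy of Section 13.9, none is powered, and Section 13.10.3 presents t-test p-values at each time as descriptive. Other between-arm safety analyses exist: Fisher tests on treatment-emergent events, which include clinically significant ECG abnormalities, and the covariate-adjusted Poisson model. The DSMB also reviews safety data every 4 months. All of this supports low severity.

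Three stronger readings are tempting, and the documents support none of them.
- A reader might infer that the plan ignores its baselines. It does not: the change scores, shift displays, treatment-emergence rule and within-arm tests all use them. Only covariate adjustment is missing.
- A reader might take 15% to 35% less variance as an established gain at no cost. That range is (1-r)/2 for r of 0.7 down to 0.3 with equal SDs, both assumed. It does not apply to the Fisher tests, and there is a small cost. BARS in particular may have unequal SDs if pre-treatment scores sit near the floor.
- A reader might take 29% against 55% power as the loss from the Fisher tests. That is the worst row of an assumed table. Exclusions for QTcF of 450 msec or more and for heart rate below 50 or above 105 leave few such subjects abnormal at baseline at comparable cut-offs, so the gain there is small. Incidences in Section 13.10.8 may already mean new cases.

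What survives is that no covariate is named, that the laboratory Fisher rule is not stated, and that mildly out-of-range laboratory values can be present at entry.

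**Conclusion.** The concern holds as a point about precision and clarity, not validity. For continuous safety measures, ANCOVA would reduce the variance by 35% to 5% for r of 0.3 to 0.9 with equal SDs. Over the unequal-SD cases shown above, the reduction runs from 0% to 50%. In large samples ANCOVA is never less precise than the change score. For laboratory abnormality rates, counting only new abnormalities avoids dilution, by an amount that cannot be derived from the documents. The severity is low: no primary result, alpha or sample size depends on it.

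**What to change.** 1. In Sections 8.2.5.2.1, 8.2.5.2.2, 13.7 and 13.10.8, replace the between-arm unpaired t-tests with ANCOVA using the subject's own baseline as covariate, or a repeated-measures model with baseline for measures taken at many visits. Report K/N minus K/L and K/N minus K/P with 95% intervals.
2. Name the baseline for each measure, and reconcile Section 8.2.1, Table 3, Section 8.2.5.2.3 and Section 13.10.8 on when it is taken.
3. For laboratory abnormality rates, state in Sections 8.2.5.2.3 and 13.10.8 that the between-arm Fisher test counts subjects normal at baseline who become abnormal. Keep the shift table, so that worsening in subjects already abnormal remains visible.

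**Cost.** SAP wording, a short change to the programs, and a decision on baselines that the plan needs in any case. No new data are required. The model uses one degree of freedom, and the Fisher test has a smaller denominator. Subjects without a baseline value drop out, as they already do for a change score.
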